9.4.1 Unanticipated Problem Reporting to IRB/IEC

Incidents or events that meet the OHRP criteria for unanticipated problems require the creation and completion of an unanticipated problem report form. OHRP recommends that investigators include the following information when reporting an adverse event, or any other incident, experience, or outcome as an unanticipated problem to the IRB/IEC:

- appropriate identifying information for the research protocol, such as the title, investigator's name, and the IRB/IEC project number;
- a detailed description of the adverse event, incident, experience, or outcome;
- an explanation of the basis for determining that the adverse event, incident, experience, or outcome represents an unanticipated problem;
- a description of any changes to the protocol or other corrective actions that have been taken or are proposed in response to the unanticipated problem.

To satisfy the requirement for prompt reporting, unanticipated problems will be reported to the IRB/IEC according to institutional policy. Unanticipated problems that are not adverse events will be reported to the sponsor within 2 weeks of the investigator becoming aware of the problem. Unanticipated problems that are serious adverse events will be reported to the sponsor according to Section 9.4.2.

Additional information will be provided in the study reference manual.

9.4.2 Serious Adverse Event Reporting to the Sponsor

Any AE meeting the specified Serious Adverse Event criteria will be submitted on an SAE form to the sponsor's centralized safety reporting system. This process applies to both initial and follow-up SAE reports.

For any initial SAE, whether deemed related to the study treatment or not, the investigator will complete a Serious Adverse Event Form and submit via fax or email within 24 hours of becoming aware of the event.

As a minimum requirement, the initial notification should provide the following information:

- Study number
- Patient number
- Gender
- Date of birth
- Name of investigator and full study site address
- Details of SAE
- Criterion for classification as "serious"
- Study drug code, or name if unblinded, and treatment start date and stop date, if applicable
- Date of SAE onset
- Causality assessment (if sufficient information is available to make this classification)

The sponsor will request clarification of omitted or discrepant information from the initial notification. The investigator or an authorized delegate is responsible for providing the requested information to the sponsor within 24 hours of the sponsor's request.

Initial reports of SAEs must be followed later with detailed descriptions, including clear photocopies of other documents as necessary (e.g., hospital reports, consultant reports, autopsy reports), with the study patient's personal identifiers removed. All relevant information obtained by the investigator through review of these documents will be recorded and provided to the sponsor within 24 hours of receipt of the information. If a new SAE Report Form is provided, then the investigator must sign and date the form. The sponsor may also request additional information on the SAE, which the investigator or an authorized delegate must provide to the sponsor within 24 hours of the request.

The SAE reporting contact information will be provided to all participating study sites by the contract research organization (CRO) on behalf of the sponsor before study initiation.

9.4.3 Reporting of SAEs and AEs to FDA and Other Regulatory Authorities

The sponsor or designee will be responsible for complying with mandatory reporting of safety events to the Food and Drug Administration (FDA) and other regulatory authorities.

9.4.4 Reporting of Pregnancy

Pregnancy is not regarded as an AE unless there is a suspicion that an investigational product may have interfered with the effectiveness of a contraceptive medication. Any pregnancy that occurs in a patient or a partner of a patient during study participation must be reported using a clinical study pregnancy form. To ensure patient safety, each pregnancy must be reported to the sponsor within 2 weeks of learning of its occurrence. The pregnancy must be followed up to determine outcome (including spontaneous miscarriage, elective termination, normal birth, or congenital abnormality) and status of mother and child. Pregnancy will result in immediate discontinuation from the study. . Pregnancy complications and elective terminations for medical reasons should not be reported as an AE or SAE. Spontaneous miscarriages must be reported as an SAE.

Any SAE occurring in association with a pregnancy, brought to the investigator's attention after the patient has completed the study, and considered by the investigator as possibly related to the study treatment, must be promptly reported to ITI according to Section 9.4.2.

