9.1.10 Adverse Events

The investigator is responsible for reporting all AEs that are observed or reported during the study, regardless of their relationship to study treatment or their clinical significance.

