9.1.10.1 Definition of Adverse Event

An AE is any untoward medical occurrence in a study patient administered a study treatment, whether or not considered drug related. This can be any unfavorable and unintended sign (such as an abnormal laboratory finding), symptom, or disease temporally associated with the use of a study treatment, without any judgment of causality.

The AE may be:

- A new illness;
- A worsening sign or symptom of the condition under treatment, or of a concomitant illness;
- An effect of the study medication, including comparator; or
- A combination of 2 or more of these factors.

No causal relationship with the study medication or with the clinical study itself is implied by the use of the term AE.

Surgical procedures themselves are not AEs; they are therapeutic measures for conditions that require surgery. The condition for which the surgery is required may be an AE. Planned surgical measures, if permitted by the clinical study protocol and the conditions leading to those measures are not AEs.

All AEs fall into the categories of "nonserious" or "serious" (Section 9.1.4).

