9.1.11 Serious Adverse Events

9.1.11.1 Definition of Serious Adverse Event

An SAE is defined as any untoward medical occurrence that at any dose:

- Results in death;
- Is life threatening;
- Requires hospitalization or prolongation in existing hospitalization;
- Results in persistent or significant disability or incapacity; or
- Is a congenital anomaly or birth defect.

The term "life threatening" refers to an event in which the patient is at risk of death at the time of the event; it does not refer to an event, which hypothetically might have caused death if it were more severe.

Medical and scientific judgment should be exercised in deciding whether an AE is serious. Some important medical events that may not result in death, be life threatening, or require hospitalization may be considered SAEs when they may jeopardize the patient such that medical or surgical intervention is needed to prevent 1 of the outcomes previously listed. Examples of such medical events include intensive emergency treatment for an allergic reaction, blood dyscrasias or convulsions that do not result in inpatient hospitalization, and the development of drug dependency or drug abuse.

Visits to urgent care or emergency room facilities may not warrant reporting as SAEs unless the patient is admitted to the hospital or the event meets other "serious" criteria. Events that are not clearly meeting "serious" criteria can be discussed on a case by case basis with the Medical Monitor to help the investigator determine whether the event meets "serious" criteria.

If either the sponsor or principal investigator believes that any event is serious, the event must be considered and evaluated by the sponsor for possible expedited reporting.

Clarification of the difference between "serious" and "severe":

The term "severe" is often used to describe the intensity (severity) of a specific event (as in mild, moderate, or severe myocardial infarction); the event itself, however, may be of relatively minor medical significance (such as a severe headache). This is not the same as "serious," which is based on patient/event outcome or action criteria usually

associated with events that pose a threat to a patient's life or functioning. Seriousness (not severity) serves as a guide for defining regulatory reporting obligations.

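### Protocol 9.4.4 bars pregnancy complications from AE and SAE reporting, although a complication in a treated patient can meet the protocol's own SAE definition and 24-hour reporting duty

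*Protocol*

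**What the plan says.** Protocol 9.4.4 deals with pregnancy on a dedicated form. The pregnancy must be notified to the sponsor within 2 weeks of the site learning of it, the patient is discontinued, and the outcome and the condition of mother and child are followed. The section then instructs: "Pregnancy complications and elective terminations for medical reasons should not be reported as an AE or SAE". Its next sentence makes spontaneous miscarriage an SAE. A separate paragraph begins "Any SAE occurring in association with a pregnancy" and sends such events to 9.4.2, on two conditions: the event became known after the patient completed the study, and the investigator thinks it possibly related to study treatment.

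The general safety sections are broader. In 9.1.10.1, "An AE is any untoward medical occurrence in a study patient administered a study treatment, whether or not considered drug related". In 9.1.10, "The investigator is responsible for reporting all AEs that are observed or reported during the study, regardless of their relationship to study treatment". The seriousness criteria in 9.1.11.1 include "Is life threatening", "Requires hospitalization or prolongation in existing hospitalization" and "Is a congenital anomaly or birth defect". Under 9.4.2, "Any AE meeting the specified Serious Adverse Event criteria will be submitted on an SAE form to the sponsor's centralized safety reporting system", and the initial report is due within 24 hours, whether or not the event is thought related.

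SAP 16.1.2 defines SAEs as the events marked serious on the adverse event page of the eCRF. The SAP text available has no separate rule for pregnancy events.

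**The concern.** The same event can fall under two opposite instructions. A treated patient admitted to hospital with a pregnancy complication has an event that the definitions make an SAE and that 9.4.4 tells the site not to report as an AE or SAE.

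If a site follows 9.4.4, the event does not enter the SAE route as an SAE. It would miss the expectedness assessment in 9.3.2, which is made for SAEs, and the review of serious, unexpected and related events that 9.5 names as a possible ground for suspension. It would also be missing from the SAE tables. Protocol 2.3.1 says that effects in pregnancy are not fully known and that new risks may appear, so serious events of this kind carry information. If some sites follow 9.4.4 and others follow 9.1.11.1, the same event is handled differently from site to site.

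**Working it through.** No arithmetic applies. The check sets the sections side by side and follows one event through them.

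1. **Is it an AE?** Take a treated patient who develops a pregnancy complication while still in the study. The definition in 9.1.10.1 covers any such occurrence in a treated patient and has no pregnancy exemption. Section 9.4.4 says separately that pregnancy is not normally an AE, but that statement concerns the pregnancy, not a complication of it. The answer under 9.1.10.1 is yes.

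2. **Is it serious?** If the complication requires admission or is life threatening, it meets "Requires hospitalization or prolongation in existing hospitalization" or "Is life threatening". Section 9.1.11.1 has no pregnancy exemption either. The answer is yes.

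3. **What must the site do?** Sections 9.1.9 and 9.4.2 both require notification within 24 hours, related or not. Section 9.4.4 says not to report. The two cannot both be followed.

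4. **Does the later paragraph of 9.4.4 resolve this?** It has two conditions, and both must hold.

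| When the event becomes known | Possibly related | Not thought related |
|---|---|---|
| During the study | not covered | not covered |
| After study completion | covered, sent to 9.4.2 | not covered |

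   One cell of four is covered. It is also unclear whether a patient who was discontinued because of pregnancy counts as having completed the study.

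5. **Is the on-study period empty, given that pregnancy ends treatment?** No. Section 4 asks patients who withdraw to return for a safety visit 2 weeks later, and 9.1.9 records SAEs from consent until follow-up.

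6. **Does the pregnancy form supply a deadline?** The 2-week limit runs from learning of the pregnancy. For a later complication, 9.4.4 requires follow-up but sets no reporting time.

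7. **Does the same conflict hold for terminations?** Only in part. Section 9.1.10.1 says that surgical procedures are not AEs, while the condition that made surgery necessary may be one. Leaving a surgical termination off the AE page agrees with that. The conflict lies with the medical condition behind the termination, or with a resulting admission, if sites take 9.4.4 to bar those as well.

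8. **What reaches the tables?** Under SAP 16.1.2 an event that is never entered on the adverse event page cannot appear in the SAE summary.

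**The case against.** The strongest reply is that the practical gap is small and other provisions partly cover it. Contraception is required (5.1), pregnancy is tested for at entry (5.2), participation is short, and AE collection ends with participation (9.4). The sponsor hears of every reported pregnancy and follows its outcome. Miscarriage is expressly an SAE. Section 9.1.11.1 obliges the sponsor to consider expedited reporting of any event that the sponsor or principal investigator believes serious. Section 9.4.3 leaves the sponsor's regulatory duties intact, and 9.2 gives a route for possibly related SAEs found after the observation period. All of this stands. It limits the number of events and the loss of information, but it does not tell a site which instruction to follow.

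A reader might infer four stronger points that the documents do not support.

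- *The reporting time stretches from 24 hours to 2 weeks.* The 2 weeks apply to notifying the pregnancy. No time is given for a complication, so the delay cannot be sized.
- *The paragraph on pregnancy-associated SAEs directly contradicts the bar.* That paragraph concerns events learned of after study completion and thought possibly related. It leaves a gap for other events but does not reverse the rule for them.
- *Fetal anomalies are barred from SAE reporting.* "Is a congenital anomaly or birth defect" is itself a seriousness criterion, and 9.4.4 lists congenital abnormality among the outcomes to follow. It does not exempt an anomaly. The termination should not be merged with the anomaly behind it.
- *Such events escape expedited review altogether.* Sections 9.1.11.1 and 9.4.3 keep that route open once the sponsor knows of the event.

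**Conclusion.** The inconsistency is real and is confined to one sentence of 9.4.4. As written, that sentence conflicts with 9.1.10.1, 9.1.11.1 and 9.4.2 for pregnancy complications in treated patients that meet a seriousness criterion, and for the medical condition behind a termination where that condition is serious. It does not clearly extend to partners' pregnancies. Section 9.4.4 collects those, but the AE definition covers only patients given study treatment.

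The size is few events, if any. The documents give no expected number and no figure for the delay. For each affected event the consequence is loss of the 24-hour SAE route and absence from the SAE summary, while the outcome is still followed on the pregnancy form. No efficacy conclusion changes. The conclusion assumes that sites follow 9.4.4 literally. The documents do not show whether the word *not* was intended or is a drafting slip. It is worth correcting because the rule as written works against safety reporting and the correction is cheap.

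**What to change.** Reconcile 9.4.4 with 9.1.10.1, 9.1.11.1 and 9.4.2 by replacing the barring sentence with three statements:

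- the pregnancy is tracked on the pregnancy form;
- an elective termination procedure is not itself an AE;
- any pregnancy complication, or medical condition underlying a termination, in a treated study patient that meets a seriousness criterion in 9.1.11.1 is also reported as an SAE under 9.4.2, with the timing given there.

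The limit to treated patients matters, because without it the wording would draw in partners' pregnancies. The SAP needs no change, since events entered on the adverse event page will then reach the SAE summaries under 16.1.2. The cost is a short protocol clarification and a note to sites. There is no effect on sample size, alpha or any analysis.

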9.5 Halting Rules

Individual patient participation in the study may be stopped at any time at the discretion of the investigator. Individual patient participation may also be stopped at any time at the request of the sponsor. Additionally, the sponsor may place a temporary or permanent suspension of enrollment at any site or for the entire study. Reasons for stopping or suspending patient participation and/or enrollment include, but are not limited to, violation of inclusion/exclusion criteria, major protocol deviation(s), or safety concern.

Review of serious, unexpected, and related AEs by the IRB/IEC, the sponsor, or the FDA or relevant local regulatory authorities may also result in suspension of further trial interventions/administration of study product at a site. The FDA or other local regulatory authorities and study sponsor retain the authority to suspend additional enrollment and study interventions/administration of study product for a site or the entire study, as applicable.

Although ITI has every intention of completing the study, ITI reserves the right to discontinue the study at any time for clinical or administrative reasons.

10 STUDY OVERSIGHT

10.1 External Data Monitoring Committee

In addition to the investigator's responsibility for oversight, study oversight will be under the direction of the sponsor and the Medical Monitor(s). The Medical Monitor(s) will be available in real time to review and recommend appropriate action regarding adverse events and other safety issues. Blinded safety data across sites will be monitored throughout the study. Blinded data regarding enrollment and retention, adverse events, outlier safety parameters (e.g. clinical laboratory results, ECG parameters) and other relevant parameters will be reviewed regularly. If necessary, additional steps may be taken to ensure data integrity and protocol compliance.
11 CLINICAL SITE MONITORING

The clinical monitor, as a representative of the sponsor, has the obligation to closely follow the study. In doing so, the monitor will visit the investigator and study site at periodic intervals, in addition to maintaining necessary telephone and letter contact with the investigator and study site. The monitor will maintain current personal knowledge of the study through observation, review of study records and source documentation, and discussion of the conduct of the study with the investigator and personnel.

All aspects of the study will be carefully monitored, by the sponsor or its designee, for compliance with applicable government regulation with respect to current GCP and current standard operating procedures.

12 STATISTICAL CONSIDERATIONS

A formal and detailed statistical analysis plan (SAP) will be finalized prior to unblinding the patients' treatment assignments and will provide further details regarding the definition of analysis endpoints and analysis methodology to address all study objectives. Changes made to the data analysis methods as described in the protocol will be documented in the SAP and will not necessitate a protocol amendment. All departures from the statistical analyses described in the approved protocol, whether made before or after unblinding, will be documented, and justified in the final clinical study report.

A blinded data review will be conducted prior to unblinding the patients' treatment assignments for assessing the accuracy and completeness of the study database and defining analysis sets, patient evaluability, and appropriateness of the planned statistical methods.

12.1 Sample Size Considerations

Approximately 350 patients will be randomly assigned in a 1:1 ratio to 1 of the 2 treatment arms (60 mg ITI-07 or placebo). A sample size of 350 patients randomized, which will provide approximately 326 evaluable patients (approximately 163/treatment group) assuming a 10% early discontinuation rate before the first post-dose assessment in the primary efficacy outcome measure (MADRS), will provide 85% power to detect a clinically relevant treatment difference from placebo of 3 points on the MADRS total score with ITI-007, with a common standard deviation of 9.0at an overall 2-sided significance level of 0.05.

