All safety parameters will be summarized using the Safety Analysis Set. Safety data such as reported and observed AEs, treatment emergent adverse events (TEAEs) and SAEs, clinical laboratory results, vital signs, physical and neurological examination findings, ECGs, and the different rating scales (YMRS, C SSRS, AIMS, BARS, and SAS) will be summarized by treatment group and visit. When appropriate, out of range values will be flagged in data listings and tabulated. Shift tables will be prepared for pre-specified safety measures, such as laboratory parameters, ECG and weight.

Sample Size:

Approximately 350 patients will be randomly assigned in a 1:1 ratio to 1 of the 2 treatment groups (ITI-007 60 mg or placebo). A sample size of 350 randomized patients will provide approximately 326 evaluable patients assuming a 10% early discontinuation rate before the first post-dose assessment of the primary efficacy outcome measure (MADRS). Approximately 163 patients per treatment group will provide 85% power to detect a clinically relevant treatment difference from placebo of 3 points on the MADRS total score with a common standard deviation of 9.0 at an overall 2-sided significance level of 0.05.

Schematic of Study Design:

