3.2 Study Outcome Measures

3.2.1 Primary

The change from baseline to Day 43 in MADRS total score is the primary outcome measure for the study. The MADRS is defined in Section 8.2.1 and will be assessed according to the Schedule of Events.

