5. FINAL AND INTERIM ANALYSES

5.1. BLINDED SAMPLE SIZE RE-ESTIMATION

An unplanned blinded sample size re-estimation was conducted based on a blinded data review of the efficacy data during the study. The estimated pooled standard deviation (SD) was 8.82, which was larger than what was assumed at study planning. The sample size was therefore increased to a total of 350 randomized subjects, based on an assumed SD of 9.0, to ensure 90% statistical power.

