7.1. MISSING DATA

The total and subscale scores of any assessment with more than one item, such as MADRS, CGI-BP-S, YMARS, CSSR-S, Q-LES-Q-SF, AIMS, BARS and SAS, will be derived from the individual items. Any individual missing item in any scale will not be imputed. If one or more items are missing at a visit, then the associated total score or subscale score will be set to missing.

The main objective of the analyses in this study is to evaluate treatment effect of 60 mg ITI-007 compared to placebo if the treatment is administered for the planned treatment duration. In order to evaluate this estimand in the presence of subjects that may discontinue treatment prematurely, the primary efficacy analysis will be performed based on the assumption of data being missing at random (MAR). This implies that subjects discontinuing from treatment early are considered to have unobserved values similar to the observed ones

Document: ...\ITI\ITI-007\MYA11638\Biostatistics\Documentation\SAP\ITI-007-404 SAP Final V1.0 12JUN2019.docx
Author: Version Number:1.0

Page 16 of 53

in their respective treatment group for subjects who have similar history, i.e., the distribution of the unobserved future values for subjects who had discontinued treatment is the same as the distribution of the observed values for those subjects who completed treatment, conditional on the available data prior to discontinuation.

The Mixed-Effects Model for Repeated Measures (MMRM) method will be used for the analysis of the primary and key secondary efficacy endpoints. The MMRM approach does not impute missing data but is based on all subjects included in the analysis set using all available longitudinal data (either complete or partial). This approach is based on the MAR assumption as described above.

Document: Author:

 $... \label{lem:likelihoof} \verb|MYA11638| Biostatistics| Documentation| SAP | Final V1.0 12 | JUN2019. docx | Continuous |$

Version Number: 1.0

STATISTICAL ANALYSIS PLAN: PROTOCOL ITI-007-404
Page 17 of 53

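### The stated power is not that of the Day 43 MMRM contrast: loss after the first post-dose MADRS is left out, 10% loss from 350 does not leave 326, and the SAP's 90% is not reached

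*Protocol*

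**What the plan says.** Protocol 12.1, repeated in the synopsis, plans about 350 patients randomised 1:1 and about 326 evaluable (163 per arm), "assuming a 10% early discontinuation rate before the first post-dose assessment in the primary efficacy outcome measure (MADRS". It says this sample "will provide 85% power to detect a clinically relevant treatment difference from placebo of 3 points on the MADRS total score". The calculation takes the SD to be 9.0 in both arms and tests at the two-sided 5% level.

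Protocol 3.2.1 sets the endpoint: "The change from baseline to Day 43 in MADRS total score is the primary outcome measure for the study". Clinic visits fall on Days 8, 15, 22, 29, 36 and 43 (Protocol 4). SAP 15.1.3 makes the primary test the Day 43 treatment contrast from an MMRM on the ITT set. SAP 6.3 admits a patient to that set with a single valid post-baseline MADRS.

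SAP 7.1 frames the estimand "in the presence of subjects that may discontinue treatment prematurely" and relies on a missing-at-random assumption. SAP 9 tabulates treatment discontinuation by visit interval up to Day 43. Protocol 5.5 says randomised patients who leave early are not replaced.

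SAP 5.1 reports a blinded pooled SD of 8.82 and a sample size raised to 350 randomised, "based on an assumed SD of 9.0, to ensure 90% statistical power". It does not restate the treatment difference. Neither sample-size section gives a loss rate after the first post-dose MADRS, a correlation between visits, or the basis of the 9.0 (before or after baseline adjustment).

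**The concern.** The allowance for loss stops at the first post-dose MADRS, scheduled for Day 8, but the hypothesis is tested at Day 43. A patient seen only at Day 8 is one of the 163 and is counted in the power formula as if a Day 43 score existed. The MMRM uses that patient's Day 8 score, but one early score does not carry the information of a Day 43 score. The plan expects discontinuation during treatment, yet the power statement makes no allowance for it.

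The surrounding figures also conflict. The 10% rate does not produce 326, and the protocol and SAP quote different power for the same 350 patients and the same SD. Someone who wants the power of the primary test cannot find it in either document. What is at stake is the accuracy of the power statement. The estimate, the test and its type I error are not affected.

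**Working it through.** **Inputs.** Difference 3 points, SD 9.0, two-sided alpha 0.05, 350 randomised 1:1, 326 evaluable, 10% early loss (all Protocol 12.1); blinded SD 8.82 and 90% power (SAP 5.1).

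**Formula.** Two-sample t-test with n per arm: noncentrality = 3 / (9 × √(2/n)), with 2n − 2 degrees of freedom.

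**1. The protocol's own figure.** n = 163: noncentrality 3.009, power 85.1% (85.3% by normal approximation). The 85% reproduces, with every one of the 163 counted as a complete Day 43 observation.

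**2. The evaluable count.** 350 × 0.90 = 315, or 157.5 per arm: noncentrality 2.958, power 83.9%. The 326 corresponds to a loss of 1 − 326/350 = 6.9%. Having 326 left after 10% loss would take 326/0.90 = 362.2, so 363 randomised. This mismatch alone is worth 85.1 − 83.9 = 1.2 points.

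**3. The SAP's 90%.** With no loss at all, n = 175: noncentrality 3.118, power 87.5%. Reaching 90% takes about 190 per arm. This uses the protocol's 3-point difference, since SAP 5.1 states none.

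**4. Later loss, starting from the documents' 163 per arm.** Let d be the share of the 163 with no Day 43 value and R² the share of Day 43 variance explained by earlier visits. Under missing at random, the effective Day 43 sample is

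n_eff = n / (R² + (1 − R²)/(1 − d)).

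Both d and R² are assumptions.

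| d | R² | n_eff per arm | Power, SD 9.0 | Power, SD 8.82 |
|---|---|---|---|---|
| 0 | – | 163 | 85.1% | 86.5% |
| 10% | 0.3 | 151.2 | 82.4% | 83.9% |
| 10% | 0.7 | 157.7 | 83.9% | 85.3% |
| 20% | 0.3 | 138.7 | 79.0% | 80.6% |
| 20% | 0.7 | 151.6 | 82.5% | 83.9% |

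At SD 9.0 the cost is 1.2-2.7 points for 10% later loss and 2.6-6.1 points for 20%.

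**5. Cross-check by another route.** A six-visit information matrix, with dropout spread evenly over Days 15-43 and AR(1) or compound-symmetry correlation of 0.5-0.85, gives 81.7-84.5% at 10% and 77.4-83.5% at 20% (normal approximation). Counting Day 43 completers only, which ignores what the MMRM recovers, gives 81.2% and 76.5% by the t formula.

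**6. Possible offset from baseline adjustment.** If 9.0 is unadjusted and baseline correlates 0.3 with change (an assumption), the residual SD is 9 × √(1 − 0.09) = 8.59. Power at 10% later loss is then 85.7-87.2%.

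**The case against.** The 85% is not a miscalculation: it follows from 163 per arm, 3 points and SD 9.0. Counting loss up to entry into the ITT set is also a coherent simplification, because later dropouts stay in that set and the MMRM uses their earlier visits. Early-discontinuation assessments are sought (Protocol 5.5.2) and mapped to visit windows (SAP 7). The documents supply no later-loss rate or visit correlation, so the size of the effect rests on assumed values. The SD was rounded up from 8.82, and the model adjusts for baseline, site and bipolar type. Under some plausible inputs the 85% survives 10% later loss.

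Most of this stands, and it limits the point. A reader might infer that the 85% holds only if nobody drops out after Day 8. The documents do not support that: it is true at an SD of exactly 9.0 with no covariate gain, but a smaller SD or a useful baseline covariate could restore 85%. A reader might also start from 315, apply 10% later loss, and report 81.1-82.7% as the effect of later dropout. That range includes the 1.2 points from the 315/326 mismatch, which is a different fault. Nor does later dropout explain the SAP's 90%, which fails before any loss.

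What remains is that the documents do not present the SD margin or the covariates as an allowance for dropout. At 20% loss, the offsets do not always bring power back to 85%.

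**Conclusion.** The point holds as a fault in the power statement. It does not show that the trial is too small. Neither document gives the power of the Day 43 MMRM contrast. At SD 9.0 with no covariate gain, any later loss takes power below 85%: by about 1 to 3 points at an assumed 10% and 3 to 6 points at an assumed 20%, from 163 per arm. An SD nearer 8.82 or baseline adjustment may return part or all of this, so the net shortfall cannot be fixed from the documents.

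Two parts rest on the documents' own figures, without any assumption about later loss. Ten per cent of 350 leaves 315 patients and 83.9% power, not 326 and 85%. And 90% power is not available from 350 patients at SD 9.0 and 3 points. A call for more patients does not follow from any of this.

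**What to change.** In Protocol 12.1, the synopsis and SAP 5.1:

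- Correct the mismatch between 10% loss and 326 evaluable. Either the rate or the count has to change.
- Replace the conflicting 85% and 90% with one figure for the Day 43 MMRM contrast, and state the treatment difference in SAP 5.1.
- State the assumed loss by Day 43, the assumed correlation between visits, and whether 9.0 is before or after baseline adjustment.
- Show the effect of later loss on its own line, apart from the 315/326 correction, over a range of rates.

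This takes about a paragraph in each place. It changes no analysis, and no more patients are needed. The downside is a slightly less favourable stated power.
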